## ABSTRACT

**IMatinib for PAin in Chronic Treatment of Sickle Cell Anemia (IMPACT SCA)** is a prospective, open-label Phase I/II study of imatinib to prevent pain in individuals with Sickle Cell Anemia (SCA). SCA is the most common severe inherited hematologic disorder worldwide with only one disease-modifying medication (hydroxyurea) licensed so far for its management. Although sickle hemoglobin polymerization is the initial trigger for the sickle cell shapedeformation leading to vaso-occlusive pain episodes, we have shown that increased production of reactive oxygen species (ROS) in sickle red blood cells (RBCs) and inhibition by ROS of both major RBC tyrosine phosphatases, leadsto phosphorylation of the major membrane-spanning protein, band 3. This phosphorylation results in dissociation of theRBC cytoskeleton from the lipid bilayer, release of free hemoglobin and emergence of circulating microparticles that contribute significantly to activation of the vascular endothelium and stimulation of the blood coagulation cascade, promoting the vasoocclusive events. Imatinib, a well-studied tyrosine kinase inhibitor, has been shown in our preclinicalstudies to inhibit band 3 phosphorylation in sickle RBCs and prevent the consequent microparticle release and hemolysisof these cells in vitro. We propose an early phase clinical trial of daily imatinib treatment on patients with SCA and recurrent vaso-occlusive crises to evaluate both the biochemical and clinical effects, with the goal to re-purpose this well-tolerated targeted medication for preventive management in SCA.

## STUDY FLOW DIAGRAM

**Study flow schema** with an outline of patient visits and corresponding evaluations.

## Abbreviations

AE	adverse event
ALT	alanine aminotransferase
ANC	absolute neutrophil count
AST	aspartate aminotransferase
CHR	complete hematologic response
CML	Chronic Myelogenous Leukemia
CRF	case report/record form
CS&E	Clinical Safety and Epidemiology
GIST	gastrointestinal stromal tumor
Hb	hemoglobin
HR	hematologic response
IEC	Independent Ethics Committee
IFN	Interferon alpha
IRB	Institutional Review Board
IDS	Investigational Drug Services
IP	Investigational Product
ITT	intention-to-treat
IULN	Institutional Upper Limit of Normal
NCI	National Cancer Institute
NIH	National Institutes for Health
od	omnia die / once a day
PDGF	platelet-derived growth factor
Ph +	Philadelphia chromosome positive
po	per os / by mouth / orally
PP	per protocol
PS	performance status
qd	queaque die / every day
RBC	red blood cell(s)
RBCM	red blood cell membrane
SAE	serious adverse event
SCF	stem cell factor
SCA	Sickle cell anemia
SCD	Sickle cell disease
SOP	Standard Operating Procedure
VOC	Vaso-occlusive crisis
WBC	White Blood Cell Count

[figure not shown]
## 1.0 INTRODUCTION

Sickle cell anemia (SCA) is a severe and devastating, chronic hematological disorder that affects nearly 100,000 persons in the United States and millions more worldwide. Data from 2001-2005 reveals that annual healthcare costs related to sickle cell disease management in the U.S. exceeds \$1.1 billion. While supportive care and disease-modifying therapies such as hydroxyurea have mitigated patient suffering and early death from sickle cell-related complications, many patients continue to suffer from anemia, recurrent vaso-occlusive painful episodes which lead to chronic organ damage, acute chest syndrome, and strokes. Although life expectancy for SCA patients in the western world has increased from 14 to approximately 50 years since 1973, the quality of life for survivors remains compromised by damage to their brain, kidneys, eyes, lungs and other organs. In some patients, the frequent requirement of opioids for pain episodes leads to opioid dependence, further limiting their quality of life. Pain caused by vaso-occlusion is the most frequent cause of hospitalization for patients with SCA and approximately 5.2% of patients with 3-10 painful events per year make up 33% of all hospitalizations. Pain rate also correlates with early death in sickle cell patients older than 20 years of age.

The pathophysiology of vaso-occlusive crisis in sickle cell disease is complex and involves sickling of RBCs caused by polymerization of the deoxygenated Hemoglobin S (HbS), consequent red blood cell (RBC) rigidity, impaired microvascular blood flow, ischemia-reperfusion injury, vascular endothelial cell activation and increased blood cell-endothelium interactions. Consequence of frequent vaso-occlusive events over time is end-organ damage.

Previous research has provided solid evidence that an important contribution to vaso-occlusive events in SCA derives from RBC membrane instability that leads to intravascular hemolysis and release of membrane fragments or microparticles. Blebbing-off of plasma membrane fragments not only releases RBC membrane-derived microparticles that are known to be prothrombotic, but also reduces the cell's surface-to-volume ratio, thereby concentrating HbS inside the cell and augmenting its propensity to polymerize. Concurrently, release of free hemoglobin from the fragmenting RBC activates the vascular endothelium to express adhesion receptors, thereby increasing retention of WBC and RBC in the microvasculature and further aggravating vaso-occlusive propensities.

Our studies have shown that increased reactive oxygen species (ROS) in sickle RBCs inhibit both of their major tyrosine phosphatases, leading to phosphorylation of the major membrane-spanning protein, band 3 (Figure 1). This results in dissociation of the RBC cytoskeleton from the lipid bilayer causing membrane fragmentation, microparticle release, and the escape of free hemoglobin into the bloodstream. This release of free hemoglobin and the circulating microparticles contribute prominently to activation of the vascular endothelium and stimulation of the blood coagulation cascade, respectively. Together, these two processes strongly promote the vaso-occlusive events that plague patients with sickle cell disease.

**Figure 1.** Band 3 in RBC membrane is regulated by tyrosine phosphorylation by Syk kinase and de-phosphorylation by RBC tyrosine phosphatases. ROS, which are increased in SCD, inhibit these phosphatases. The phosphorylation of tyrosines 8, 21, and 359 in the cytoplasmic loop of band 3 leads to displacement of the glycolytic enzyme complex, binding of the band 3 cytoplasmic loop to its SH2 domain and rupture of the band 3-ankyrin bridge to the RBC cytoskeleton.

Imatinib, a well-studied tyrosine kinase inhibitor, has been shown in our preclinical studies to suppress band 3 phosphorylation in sickle RBCs and to prevent the consequent fragmentation, microparticle release, and hemolysis of these cells in vitro. Additionally, in two published case-reports, patients with SCA, who incidentally developed chronic myelogenous leukemia (CML), experienced cessation of vaso-occlusive pain episodes upon initiation of treatment with imatinib for their CML, followed by recurrence of vaso-occlusive crises whenever imatinib therapy was inadvertently interrupted. Therefore, **we hypothesize that imatinib, as an inhibitor of tyrosine phosphorylation of band 3, will ameliorate SCA symptoms by preventing RBC membrane destabilization and consequently intravascular hemolysis and microparticle release, which in turn would activate adhesion receptors on the endothelium and trigger the coagulation cascade, respectively.** Since imatinib is approved for use in children and can be taken for years without serious adverse events, we hypothesize that it could constitute a well-tolerated treatment for SCA that will function by a novel mechanism to inhibit vaso-occlusive crisis, pain, and chronic organ damage.

## 2.0 RATIONALE FOR DEVELOPMENT

Although preventive and supportive management, including prophylactic antibiotics to prevent serious infections from encapsulated organisms, opioids and non-steroidal anti-inflammatory medications to control painful episodes, blood transfusions to dilute out sickle RBCs, and hydroxyurea as a fetal Hgb inducer and disease-modifying therapy have mitigated patient suffering and extended life expectancy of patients with SCA, many patients still continue to suffer from anemia and recurrent vaso-occlusive painful episodes which lead to chronic organ damage and compromise quality of life. Bone marrow transplant, and in clinical trial settings gene therapy are curative treatments, available in US and Europe, but are not feasible for all patients and not free of undesirable toxicities. New experimental therapies in the pipeline include new fetal Hb inducers, nitric oxide generators, statins and drugs that elevate the affinity of hemoglobin for oxygen. Unfortunately, each of the well-established therapies (even hydroxyurea as monotherapy) may have limited efficacy or undesirable toxicities, while many of the experimental therapies, though promising in some cases, will likely require years before they can be routinely implemented in sub-Saharan Africa, for example, where 75% of the sickle cell patients reside.

Clearly, the need for more, safe, easily administered, inexpensive and effective SCA therapeutic options is high, in order to improve morbidity and early mortality in the 14 million patients suffering of sickle cell disease across the world. In this protocol, we will explore whether imatinib can inhibit *in vivo* a tyrosine kinase-mediated mechanism that induces erythrocyte membrane destabilization, an important biological factor in the clinical manifestations of sickle cell disease. Results from this study will inform a future Phase II-B trial with imatinib to assess clinical outcomes in patients with sickle cell disease.

## 3.0 BACKGROUND

### 3.1 Vaso-Occlusion and Sickle Cell Disease

Sickle cell disease is characterized by recurrent attacks of vaso-occlusive painful events that often manifests as severe pain, acute chest syndrome, or priapism. Approximately 5.2% of patients with 3-10 painful events per year make up 33% of all hospitalizations. Pain rate also correlates with early death in sickle cell patients older than 20 years of age. The pathophysiology of vaso-occlusion in sickle cell disease is complex, and involves not only the “sickling” of RBCs due to polymerization of deoxygenated HbS, but also increased cellular adhesiveness of sickle RBCs. Previous research has provided solid evidence that an important contribution to vaso-occlusive events in SCD derives from the RBC membrane instability that leads to intravascular hemolysis and release of membrane fragments or microparticles.

 Blebbing off of plasma membrane fragments not only releases RBC membrane-derived microparticles that are known to be prothrombotic, but also reduces the cell's surface-to-volume ratio, thereby concentrating HbS inside the cell and augmenting its propensity to polymerize. Concurrently, release of hemoglobin from the fragmenting RBC increases free heme in the circulation which activates the vascular endothelium to express adhesion receptors, thereby increasing retention of WBC and RBC in the microvasculature and further aggravating vaso-occlusive propensities.

The organ failure and extreme pain commonly associated with SCD derive to a substantial degree from the above obstruction of blood vessels and associated inflammation. In search for a safe and effective SCD therapy with a novel target mechanism, we have focused on finding a method to stabilize the RBC membrane against the vesiculation and intravascular hemolysis that have been shown to contribute to the development of vaso-occlusion and subsequent clinical manifestations of SCD.

[figure not shown]
### 3.2 Preclinical Studies with Imatinib

Our preclinical studies have implicated phosphorylation of band 3 in the RBC membrane as integral to the development of vaso-occlusive events in patients with SCA (Figure 1). Band 3 is phosphorylated by the tyrosine kinase Syk, which can be inhibited by imatinib.

Some of the initial steps in the chain of molecular events leading to vascular obstruction and pain crisis in patients with sickle cell disease are the following:

- 1) sickle erythrocytes have elevated levels of Reactive Oxygen Species (ROS) generation due to auto-oxidation of Hb S that denatures into hemichromes (partially denatured Hb complexes preceding Heinz body formation), as well as due to increased production of ROS by erythrocyte NADPH oxidase which is activated by inflammatory cytokines
- 2) ROS inhibit both of the RBC's major tyrosine phosphatases which have active site cysteines that are highly sensitive to oxidants (Figure 1)
- 3) in the absence of functioning tyrosine phosphatases, the major membrane-spanning protein, band 3, becomes phosphorylated on tyrosines 8, 21, and 359 by Syk tyrosine kinase
- 4) this phosphorylation of band 3, which is absent in healthy HbA erythrocytes (Figure 2), causes dissociation of the RBC cytoskeleton from the lipid bilayer, leading to membrane weakening and fragmentation, leading to a storm of microparticle release (Figure 3) and free hemoglobin escape into the bloodstream

As noted above, this release of free hemoglobin and circulating microparticles contributes prominently to activation of the vascular endothelium and stimulation of the blood coagulation cascade, respectively. Together, these two processes strongly promote the vaso-occlusive events that plague patients with SCD. Based on these considerations, we hypothesized that a tyrosine kinase inhibitor that inhibits Syk and blocks tyrosine phosphorylation of band 3 on tyrosine 8, 21, and 359 will ameliorate the symptoms of SCD by preventing RBC membrane destabilization and the consequent intravascular

**Figure 2.** Anti-phosphotyrosine immunoblot of band 3 protein in control and sickle red blood cells before and after treatment in vitro with 1  $\mu$ M imatinib for 3 hours. C= Control cells; C+I= Control cells + Imatinib; S= sickle cells; S+I= Sickle cells + Imatinib. Data with samples from five different patients with Sickle Cell Disease. Note the strong tyrosine phosphorylation of band 3 in sickle cells and the paucity of phosphorylation in normal cells at baseline.

hemolysis, microparticle release, and decrease in RBC surface-to-volume ratio that enhances RBC sickling and vaso-occlusion.

In search for a tyrosine kinase inhibitor that might suppress the tyrosine phosphorylation of band 3 in sickle cells, we screened Eli Lilly's tyrosine kinase library (provided by [name] of Eli Lilly) for suppressors of band 3 tyrosine phosphorylation. Five kinase inhibitors were found to potently inhibit the aforementioned band 3 tyrosine

phosphorylation. Importantly, when the identities of the inhibitors were revealed to us at the end of the study, one inhibitor stood out from the rest because it was already approved by the FDA for use in children. This tyrosine kinase inhibitor was imatinib (Gleevec), an orally bioavailable inhibitor of a group of tyrosine kinases, including Bcr-Abl, PDGFR, and c-Kit, that is employed for treatment of chronic myelogenous leukemia (CML), gastrointestinal stromal tumors, clonal hypereosinophilic syndrome and D816V-negative mastocytosis. Most relevant to the proposed study, however, is the fact that even though imatinib must be taken by CML patients daily for the rest of the patient's life (or until resistant mutations emerge), it has an excellent safety record with limited adverse events. Based on these considerations, imatinib was selected as a medication possible to be re-purposed for SCD, with the goal to inhibit band 3 tyrosine phosphorylation, RBC membrane vesiculation, microparticle formation and hemolysis and interrupt the chain of molecular events aggravating vaso-occlusion.

### 3.3 Clinical Experience with Imatinib

Two highly relevant sets of studies in which imatinib has been intentionally or unintentionally used to treat an erythrocyte-related disease should be mentioned here.

#### 3.3.1 Imatinib to treat *P.falciparum* malaria

First, imatinib has been used to treat *P. falciparum* malaria both in human whole blood cultures of the parasitemia *in vitro* and in malaria patients in Vietnam *in vivo*. Importantly, imatinib was selected for this application because the malaria parasite induces band 3 tyrosine phosphorylation shortly before its egress from the erythrocyte during its intra-erythrocyte life cycle. The parasite does this in order to weaken the RBC membrane to facilitate its escape from its host RBC (i.e. the parasite exploits

[figure not shown]
the same tyrosine kinase-induced RBC membrane destabilization seen in SCA). Both in *in vitro* studies and in the clinical application *in vivo*, imatinib was successful in blocking band 3 tyrosine phosphorylation and parasite egress, thereby terminating the parasitemia. Moreover, no drug related adverse events have been observed to date in malaria patients treated with imatinib.

#### 3.3.2 Imatinib to treat SCA patients with CML

The second relevant set of studies concerns the use of imatinib to treat CML in patients who coincidentally also suffered from SCA. Anticipating that someone with SCA must have at some time contracted CML, we scrutinized the literature for case reports of SCD patients who were treated with imatinib to control their CML. Two such case reports were found. Importantly, upon treatment with imatinib, none of the patients in either of the papers experienced any further symptoms of SCA. In fact, in one published report, the investigator noted that if the patient missed several days of imatinib, vaso-occlusive crises recurred, and stopped "immediately when the patient took imatinib again". The authors of one of the articles speculate that imatinib may somehow suppress inflammatory cells, but they offer no data to support this hypothesis. Based on our data, we hypothesize that imatinib treatment of those patients prevented SCA- associated vaso-occlusive painful events via inhibition of Syk-induced RBC membrane destabilization.

### 3.4 Overview of Proposed Study

In this protocol, we propose to evaluate the biochemical effects of imatinib on sickle RBCs. Patients will be administered imatinib mesylate orally following the guidelines previously established for use of imatinib in other

**Figure 3.** Incubation of RBCs with ortho-vanadate (O-V, phosphatase inhibitor) for increasing time intervals induces membrane vesiculation (A) associated with band 3 tyrosine phosphorylation (B). C. Glycophorin A (GPA)-positive microparticles, derived from RBC membrane, determined by flow cytometry in the plasma of patients with sickle cell disease versus normal control (HbA) volunteers. GPA is a sialoglycoprotein that spans the RBC membrane and is easily identified by flow cytometry.

disorders. The biochemical effects of imatinib on sickle RBCs will be examined, including changes in their levels of band 3 tyrosine phosphorylation and the abundances of RBC-derived microparticles in their blood. In addition, the patients will be monitored for symptoms of SCD. As noted in Fig. 2, we expect band 3 tyrosine phosphorylation to decrease dramatically in patients treated with imatinib. We also anticipate a reduction in the numbers of RBC-derived microparticles in circulation (quantitated by assaying the number of glycophorin A positive microparticles in peripheral blood samples by flow cytometry; see Fig. 1). Most importantly, we expect to see a reduction in the frequency of vaso-occlusive crises, and possibly acute chest syndrome and utilization of opioids. The study duration is planned as 6 months in order to provide adequate time for potential change in the primary endpoints (e.g. percent irreversibly sickled cells).

## 4.0 STUDY OBJECTIVES

### 4.1 Primary Aims

- 4.11 To examine the biochemical effects of imatinib by:
  - a. quantitation of band 3 phosphorylation and microparticle release from sickle RBCs
  - b. functional RBC analysis

As noted in Figure 2, we expect band 3 tyrosine phosphorylation to decrease dramatically in patients treated with imatinib. We also anticipate a reduction in the numbers of RBC-derived microparticles in circulation (quantitated by assaying the number of glycophorin A positive microparticles in peripheral blood samples by flow cytometry; see Figure 3B). We will evaluate for improvement in the red cell cytoskeleton mechanics by ektacytometry (which should improve due to reduced loss of RBC membrane as a consequence of decreased band 3 phosphorylation), oxygenscan, and determination of percent irreversibly sickled cells.

### 4.2 Secondary Aims

- 4.21 To assess the effect of imatinib on the frequency of vaso-occlusive pain events in patients with sickle cell disease
- 4.22 To assess the effect of imatinib on the amount of opioid use, frequency of acute chest syndrome, and number of hospitalizations
- 4.23 To assess the tolerability and toxicity of imatinib in patients with sickle cell disease

The clinical outcome will be a secondary aim due to the relatively short duration of the study; we expect to see a reduction in the frequency of vaso-occlusive crises, utilization of opioids, and number of hospitalizations and possibly in the incidence of acute chest syndrome and other SCA-associated complications.

### 4.3. Endpoints

- 4.31 Primary Endpoints:
  - a. Biochemical Effects to RBCs (see Section 17)
    - i. Band 3 Phosphorylation
    - ii. Microparticle Release
  - b. Functional RBC analysis (see Section 17)
    - i. Percent Irreversibly Sickled Cells at Month 6
    - ii. Ektacytometry
    - iii. OxygenScan to evaluate for altered susceptibility to sickling
- 4.32 Secondary Endpoints:
  - a. Clinical Outcomes

- i. Vaso-occlusive Crisis (VOC)
  - i. Defined as an acute episode of pain lasting greater than 24 hours, with no medically determined cause other than a vaso-occlusive event that resulted in treatment with oral or parenteral opiate agents and/or parenteral nonsteroidal anti-inflammatory agents.
  - ii. To be documented in pain diary by patient/guardian and reviewed at each visit
  - iii. Measured by pain scale (1-10) or Wong-Baker Faces scale based on age:
- ii. Acute Chest Syndrome
  - i. Defined as respiratory distress (hypoxia, shortness of breath, chest pain, tachypnea) with evidence of an infiltrate on chest x-ray
  - ii. Will be reviewed at each visit, as well as extracted from the EMR by each site
- iii. Opioid Use
  - i. Defined as both oral and parenteral opioid use
  - ii. Oral use will be documented in pain diary by patient/guardian and reviewed at each visit.
  - iii. Frequency of refills and parenteral opioid use will be extracted from the EMR by each site
- iv. Hospitalizations
  - i. Defined as an emergency room or clinic visit resulting in an inpatient admission or observation for a sickle cell-related event (e.g. vaso-occlusive pain, acute chest syndrome, etc).
  - ii. Will be reviewed at each visit, as well as extracted from the EMR by each site
- v. Assessment of tolerability and evaluation for any toxicities of imatinib in patients withSCA

## 5.0 INVESTIGATIONAL PLAN

### 5.1 Study Design

This will be an open label nonrandomized pilot study to determine the effect of imatinib on band 3 phosphorylation, microparticle release from sickle RBCs, and percent irreversibly sickled cells obtained from adolescent and young adult patients with Hemoglobin SS Disease or S-Beta 0 Thalassemia before, during, and after 6 months of treatment with imatinib. We will also look at clinical outcomes during treatment (pain) and before treatment. Clinical outcomes before treatment will be collected via retrospective chart review.

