Patients will be given a copy of the "Patient Pain Journal" at each visit which will need to be completed and returned at the next visit. This journal should be reviewed with the treating physician and/or research nurse at each clinic appointment while on study. Patients should be instructed to use the journal to record any occurrence of pain episodes (see definition in Section 5.3), the duration, and necessary interventions. They will be asked to score their pain on a scale of 1-10. Additionally, it will be used to record the date and time of each imatinib dose as well as observed side effects and supportive treatments used while on study.

Opioid use, hospitalizations, and occurrence of acute chest syndrome (see definitions in Section 5.3) will be reviewed at each study visit, as well. This information will also be extracted from the EMR at each site to confirm patient/guardian report.

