## **13.0 CRITERIA FOR REMOVAL FROM PROTOCOL THERAPY**

1. Adverse Events requiring removal from study
2. Refusal of further protocol therapy by patient/parent/guardian.
3. Non-compliance that in the opinion of the investigator does not allow for ongoing participation, including <70% of drug prescribed being taken. Compliance will not be contingent on completion of the pain journal as this not the primary endpoint of the study.
4. Physician determines continued protocol therapy is not in the patient's best interest.

Patients who are off protocol therapy are to be followed until they meet the criteria for Off Study (see below). Ongoing adverse events, or adverse events that emerge after the patient is removed from protocol therapy, but within 30 days of the last dose of investigational agent, must be followed and reported via RDE and AERS (if applicable). Follow-up data will be required unless consent is withdrawn.

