### **18.4 Study Data Management**

Primary data will be collected from treatment or test results included in the subject's medical record or source documentation given by the subject (i.e., patient diary). Patients will be registered in OnCore. Data will be entered on the Case Report Forms (CRFs) developed for this study stored electronically in REDCap. This database will be backed up automatically every week. Quality assurance steps will include: 1) built-in range checks; 2) testing of the database by the study team prior to moving to production mode; and 3) review and verification of all by the principal investigator and the research manager. Specific data questions will be given to the appropriate personnel who will then investigate and resolve the questions with the help of the investigator as necessary. Additionally, the following quality control methods will be used: 1) single entry of data with random checks of accuracy; and 2) extraction and cleaning of data that will be used for analysis every 6 months.

Data will be recorded on the CRFs and will be kept confidential with only the principal investigator, co-investigators, statisticians, IRB and the research personnel having access to individually identifiable data. The CRFs will be locked in a cabinet in a secure area with limited access to the building.

Data from this study will be retained for a minimum of 7 years for health data per Indiana State law. Following this period, paper will be shredded and permanently deleted from any computers.

Identifiable data will be shared only between research team members approved on the "Investigator List" in any of the following ways: encrypted email, US postal service or trackable courier services (i.e. FedEX), fax in a secured area, shared drive with password protection, personal delivery by authorized research personnel and/or private telephone conversations to authorized personnel.

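### Vaso-occlusive crisis frequency is counted from charts before treatment but from a patient diary on treatment, and the look-back window is not stated

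*Combined protocol and SAP*

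**What the plan says.** Section 5.1 covers the pre-treatment side for all clinical outcomes in one sentence: "Clinical outcomes before treatment will be collected via retrospective chart review". It gives no length or dates for the look-back.

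On treatment, section 4.3 says of VOC: "To be documented in pain diary by patient/guardian and reviewed at each visit". Section 6.0 describes a pain journal handed out at each visit, "which will need to be completed and returned at the next visit", and reviewed with the physician or research nurse. The VOC definition in 4.3 includes episodes of more than 24 hours treated only with oral opiates, so an episode managed entirely at home counts.

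The other clinical event outcomes have an EMR source on treatment. For opioids, 4.3 says "Frequency of refills and parenteral opioid use will be extracted from the EMR by each site"; acute chest syndrome and hospitalizations are also to be extracted from the EMR. Section 6.0 repeats the list: "Opioid use, hospitalizations, and occurrence of acute chest syndrome (see definitions in Section 5.3) will be reviewed at each study visit, as well", and adds that this information is also taken from the EMR as confirmation. VOC is in neither list. Section 18.4 names both the medical record and the diary as data sources without assigning VOC to either. Section 13.0 adds: "Compliance will not be contingent on completion of the pain journal as this not the primary endpoint of the study".

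Entry requires at least 2 documented VOCs in the prior year (5.2.1). All patients form one treated group for 6 months (6.0). Section 15.4 lists McNemar, Cochran-Mantel-Haenszel-type, paired t and Wilcoxon tests for count outcomes, to be chosen by distribution, and mentions no baseline period or person-time.

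**The concern.** A before/after comparison of event counts needs the same event, found in the same way, on both sides. Here a chart is compared with a diary. An episode treated at home can be invisible to the chart before treatment and visible to the diary afterwards, which looks like a rise. An episode never written down and not recovered at a visit looks like a fall. There is no control group in which either artefact would show.

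The missing window raises a second issue. Patients are admitted because they had at least 2 VOCs in a given year. If that year, or part of it, is also the baseline, the baseline is selected to be high and some fall is expected without any drug effect.

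The stakes are modest but real. Section 4.2 expects fewer VOCs, section 3.4 singles this out as the most important expectation, and section 2.0 says the results will inform a Phase II-B trial of clinical outcomes.

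**Working it through.** **The plan's own figure.** The documents state no power or rate for VOC. The only power figure is 89% for microparticles (15.1). The SD of the difference is 75,000 × √(2 × (1 − 0.5)) = 75,000, and the noncentrality is (70,000/75,000) × √20 = 4.17. With 19 df and two-sided alpha 0.01 the exact noncentral t gives 0.890. It reproduces and is not at issue here.

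**1. Source mismatch.** Let h be the share of VOCs treated at home, c the share of those that charts capture, and g the completeness of the diary after visit review. VOCs leading to admission or parenteral opioids are taken to be in the chart. Then

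ratio of diary to chart count = g / [(1 − h) + h × c].

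None of these shares is in the documents. The assumed ranges are h = 0.2 to 0.6, c = 0.5 or 1, g = 0.7 or 1.

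- h = 0.2, c = 0.5, g = 1: 1/0.9 = 1.11
- h = 0.4, c = 0.5, g = 1: 1/0.8 = 1.25
- h = 0.6, c = 0.5, g = 1: 1/0.7 = 1.43, an apparent rise of 43%
- h = 0.4, c = 0.5, g = 0.7: 0.7/0.8 = 0.875
- c = 1, g = 0.7: 0.70, an apparent fall of 30%

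With no drug effect the comparison can move either way.

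**2. Selection, only if the baseline is the qualifying year.** Assume each patient has a stable annual rate, gamma distributed across the clinic with mean m and shape k, and Poisson counts N given the rate. Patients enter if N ≥ 2. With no drug effect,

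apparent fall = 1 − E[rate | N ≥ 2] / E[N | N ≥ 2].

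Example with m = 3, k = 1: P(0) = 1/4 = 0.25, P(1) = 0.75 × 0.25 = 0.1875, so P(N ≥ 2) = 0.5625. E[N | N ≥ 2] = (3 − 0.1875)/0.5625 = 5.00. The expected rate given N = y is 0.75 × (y + 1), so E[rate | N ≥ 2] = (3 − 0.25 × 0.75 − 0.1875 × 1.5)/0.5625 = 4.50. The fall is 1 − 4.50/5.00 = 10.0%.

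The last column gives simulated trials of n = 20 completing 6 months, with the on-treatment count annualised and compared by paired t-test. False benefit means two-sided p < 0.05 toward a fall (nominal 2.5%).

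| Assumed clinic mean per year | Apparent fall, k = 0.5 / 1 / 2 / 4 | False benefit |
|---|---|---|
| 2 | 11.8 / 16.7 / 21.4 / 25.3% | about 14–31% |
| 3 | 7.3 / 10.0 / 12.3 / 13.9% | about 9–14% |
| 4 | 5.1 / 6.7 / 7.7 / 8.1% | about 7–9% |
| 8 | 2.0 / 2.2 / 1.9 / 1.4% | about 4–5% |

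A shorter window inside the qualifying year carries the same proportional fall if events are spread evenly over the year.

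**3. Together.** The two effects multiply. At m = 3, k = 1, a diary/chart ratio of 1/0.90 = 1.11 cancels the selection fall exactly, and a larger ratio turns it into a rise. The net direction cannot be known in advance.

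**The case against.** The diary is not left unattended. Section 6.0 requires the journal to be returned and reviewed, and takes an interim history at monthly visits. Table 2 in section 11.0 lists history at each of them. Section 13.0 says only that an incomplete journal is not non-compliance. Many missed entries could therefore be recovered, and the 70% completeness used above is an assumption without support in the text. This stands, and it narrows the low end of the ratio. It does nothing for home-treated episodes missing from pre-treatment charts.

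VOCs that lead to admission or parenteral opioids leave an EMR trace in both periods. This also stands, and it confines the mismatch mainly to home-treated episodes.

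VOC is a secondary outcome of an open-label pilot, unpowered and tied to no decision rule, and a single-arm change is weak evidence even when measured well. That limits the consequence to how a VOC change is read.

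Stronger readings are tempting, and the documents do not support them:

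- A reader might infer that raw 12-month counts will be set against raw 6-month counts, which alone would show a 50% fall. Neither 5.1 nor 15.4 proposes this, and an analyst would be expected to scale.
- A reader might infer that the baseline is the qualifying year. That year is the only one-year look-back in the documents, but it is never named as the baseline.
- A reader might infer that McNemar's test could only point to a fall. That needs both a qualifying-year baseline and a cut at 2 or lower; dichotomising is only one of three options in 15.4.
- A reader might infer that the plan is tilted toward benefit. The sign of the source bias is unknown.

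**Conclusion.** The concern holds for VOC frequency only. The source mismatch follows from what the plan states: charts before treatment, diary on treatment, and EMR extraction written for the other clinical events but not for VOC. Its size rests on assumed capture shares and runs from an apparent 30% fall to an apparent 43% rise with no drug effect.

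The selection effect is conditional on a window the plan does not state. If the baseline lies in the qualifying year, the expected fall is 12–25% at an assumed clinic mean of 2 per year, 7–14% at 3, 5–8% at 4 and 1–2% at 8. These figures assume stable gamma-Poisson rates. The documents give no VOC rate for enrolled patients, so no row can be singled out.

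Confidence is high that the sources differ and the window is missing; it is not high for any particular size or direction. The five laboratory primary endpoints and their power statement are untouched. As written, neither a fall nor a rise in VOCs could be read as a drug effect. The fix is cheap enough to be worth making.

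**What to change.** In sections 5.1 and 15.4, for VOC:

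1. For the before/after comparison, extract chart/EMR-documented VOCs in both periods with the same rule. One workable rule is episodes with an acute-care encounter or parenteral treatment, excluding episodes charted only because the journal was reviewed at a study visit. Without that exclusion the monthly visits themselves would raise on-treatment charting.
2. State the look-back window and express both periods as a rate per person-time, with one method of comparison named in advance.
3. Report diary VOCs that meet the protocol definition, including home-treated ones, separately as an on-treatment description.
4. If the baseline overlaps the qualifying year, report the change as descriptive, state the expected regression to the mean, and do not dichotomise VOC at 2 or lower against that year. A baseline from months 13–24 before entry is an optional sensitivity analysis where charts allow; those charts may be less complete or reflect different background care.

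The cost is a few sentences and a small amount of extra extraction for 20 patients whose EMRs are already being searched for the other outcomes. The price in information is fewer events in the chart-only comparison, with home-treated episodes outside it.
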